4.0 Recruitment Methods

4.1 Identification of subjects

Patients who present to the Emergency Department (ED) or who are already hospitalized at Hershey Medical Center (HMC) will be identified via the "brain attack" alert system. This system is updated in real-time when patients are having an acute IS in the ED or on the inpatient services of hospital. All stroke attending team physicians, residents, stroke fellows, the clinical stroke team and the stroke research coordinators are paged. All study personnel for this study have access to the brain attack alert system and will be notified. Upon presentation, all stroke patients have a neurological examination and are assessed using the NIHSS and the mRS as part of their routine care.

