7.2 Study Procedures

7.2. 1 Baseline

Baseline activity will occur within 18 hours of symptom onset (or last known well time) and will include screening, enrollment, randomization, medical history, physical and neurological examinations, clinical assessments (including the NIHSS, mRS, BI, GCS and MOCA), collection of blood biomarkers and liver function tests.

1. **Screening and Enrollment:** The study will enroll participants over one year. Each patient in the ED or on the inpatient service who presents with acute stroke-like symptoms and/or suspected cerebral infarction within 18 hours of symptom onset or their last known time being well, will be identified and screened for the study. The time of symptom onset will be determined based on discussion between the clinical care team and the patient, the patient's care givers and the treating physicians. If the stroke onset time is not known, such as when a patient awakens with stroke symptoms, the last known time when the patient was well will be defined as onset time. Acute ischemic stroke (AIS) will be diagnosed based on non-contrast head CT, perfusion head CT and/or brain MRI or based on neurological assessment, all of which is part of the routine assessments by the clinical physician team. The severity of stroke will be determined by the NIHSS and mRS, which are completed by the treating physicians at time of presentation.

Prior to performing any study-related activities, written informed consent will be obtained from the subject or the subject's LAR. The background of the proposed study, all study procedures, the benefits and risks of the study, and that study participation is voluntary for the subject will be explained to the subject or the subject's LAR, who will be given sufficient time to consider whether to participate in the study.

After obtaining written consent, the subject's data will be collected from the medical record for research purposes.

2. **Randomization:** After obtaining written consent, subjects will be randomized to either the PGZ or placebo treatment arm of the study using an equal allocation ratio (1:1). See section 7.4.3.
3. **Pretreatment assessments:** Prior to the administration of the investigational product, the following will be done.

The following standard of care data will be **collected from the EMR for research purposes:**

- Demographic information (age, gender, race, contact information)

- Medical history
- Admission diagnoses

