- Time of symptom onset or last known well time
- Current medication usage
- Results from the standard care laboratory workup including complete blood count, coagulation studies, basic metabolic panel (including serum glucose, renal function, and electrolytes), and if applicable results of pregnancy test and urinary drug screen)
- Health care services rendered (diagnostic workup procedures, use of t-PA, and thrombectomy, use of antibiotics, treatment of cerebral edema and hemorrhagic conversion)
- Images and results of the interpretation of the neuroimaging studies (brain MRI and head CT)
- NIHSS and mRS scale

The following assessments will be **performed only for research**:

- BI, GOS will assess neurological outcomes and will be performed by certified study personnel.
- MOCA will assess cognitive function and will be performed by certified study personnel.
- Blood will be collected (approximately 15 mls.) for the following tests:
 - ESR, hsCRP, CBC with differential, blood glucose, insulin, cortisol and catecholamines
 - T Cells, B cells, activated myelocytes
 - Inflammatory markers, cytokines, apoptotic markers
 - Other biomarkers.
 - AST, ALT and total bilirubin

4. Administration of the Investigational Product: Study treatment administration will be initiated within 18 hours after the onset of stroke symptoms or last known well time. Liver function tests (serum ALT, AST, and total bilirubin) will be assessed prior to initiating study drug treatment. The treatment group will receive a 45 mg Pioglitazone capsule orally every 24 hours for 3 days for a total of 3 doses. The control group will receive placebo at the same time points. Both groups will be treated identically and receive best standard of care.

If subject will be unable to swallow the study drug, will be administered via feeding tube (See study drug detailed in sections 7.4.2 and 7.4.5).

In addition, for research purposes finger stick glucose measurements will be performed 2h after initial study drug administration (time of peak of PGZ concentration) and subsequently at regular time points as determined by the standard of care protocol for stroke patients (see attached standard of care protocols for hypoglycemia and hyperglycemia for acute stroke patients, Appendix 1).

7.2. 2 Day 1

This will occur 24 (+/- 2) hours after the initial dose of the investigational product is administered. At this time, the following **research-only activities** will occur:

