This visit will occur 90 days (+/- 30 days) from the day of discharge. A standard of care routine physical and neurological examination will be conducted. If the patient is unable to travel to the clinic, the following assessments may be done via phone call:

- NIHSS and mRS scale
- BI, GOS (for research only)
- MOCA (for research only)
- AEs and concomitant medications will be documented for **research-only**.

Schedule of Study Activities

	Baseline (0-18h from symptom onset)	Day 1: 24+/-2h after first dose of study drug/ placebo 24 hrs	Day 2: 24+/-2h after second dose of study drug/ placebo	Day 3: 24+/-2h after third dose of study drug/ placebo	Discharge	Day 90: ± 30 days follow-up visit

Screening/Enrollment	X					
Informed consent	X					
Administration of study drug or placebo	X	X	X			
Clinical scales: NIHSS, mRS, BI, GOS, MOCA	X				X	X
Blood for laboratory tests and biomarkers	X (pre-treatment)	X (pre-treatment)	X (pre-treatment)	X		
Liver function test	X (pre-treatment)		X (pre-treatment)			
Medical history	X (pre-treatment)					
Physical and neurological examination	X (pre-treatment)				X	X
AEs and concomitant Medications		X	X	X	X	X
Blood glucose assessment via finger stick	X*					

BI = Barthel Index; GOS = Glasgow Outcome Scale; MOCA = Montreal Cognitive Assessment; mRS = modified Rankin Scale; NIHSS = NIH Stroke Scale

*finger stick glucose measurements will be performed 2h after initial study drug administration (time of peak of PGZ concentration) and subsequently at regular time points as determined by the standard of care protocol for stroke patients (see attached standard of care protocols for hypoglycemia and hyperglycemia for acute stroke patients, Appendix 1).

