7.3 Duration of Participation

The total duration of study participation for each subject will be approximately three months, which consists of:

- Screening and enrollment period (within 18 hours of stroke symptom onset)
- Treatment period of 72 hours (3 days)
- A 90 day follow-up visit occurring during the standard of care outpatient visit to the neurology clinic.

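### The Day 90 phone option covers NIHSS and MOCA, which cannot be fully scored by voice, with no telephone version, unscored-item rule or record of mode

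*Combined protocol and SAP*

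**What the plan says.** Section 7.3 describes the Day 90 contact as a clinic visit: "A 90 day follow-up visit occurring during the standard of care outpatient visit to the neurology clinic". Section 7.2.6 plans an in-person examination ("A standard of care routine physical and neurological examination will be conducted") and then gives the exception: "If the patient is unable to travel to the clinic, the following assessments may be done via phone call". The first entry in the list that follows is "NIHSS and mRS scale"; BI, GOS and MOCA come next. The exception does not separate scales that rest on an interview from scales that rest on examination or on visual tasks. The Schedule of Study Activities puts all five scales in one row.

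At admission the mode is different. Section 7.2.1 says: "The severity of stroke will be determined by the NIHSS and mRS, which are completed by the treating physicians at time of presentation". For cognition it says: "MOCA will assess cognitive function and will be performed by certified study personnel".

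NIHSS and MOCA are both named under the first objective in Section 1.1, and outcome at three months is the first primary objective in Section 1.2. Section 8.3 compares the arms on the change in the neurological scales from admission to three months, using a mixed model with a cumulative logit link.

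**The concern.** A voice call does not let an assessor observe limb drift, gaze, visual fields or sensation, or administer drawing and picture tasks. That follows from what the two instruments are; the protocol does not list their items. An assessor who follows Section 7.2.6 for a phoned patient must therefore improvise: leave items blank, carry forward the last examination, ask the patient or carer, or assume a value. The plan does not say which, and different assessors may choose differently.

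Two things are at stake. First, the analysed quantity is a change from admission. For a phoned patient it mixes recovery with a change in how the scale was obtained. Second, the reason for phoning arises after randomisation and may be tied to recovery, so the affected values need not be a random subset. If mode is not recorded, these values cannot later be separated from clinic scores. Section 8.2 says the pilot data will feed the power analysis of a later trial, so distorted means and spreads would carry forward.

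**Working it through.** The plan states no figure that depends on this point, so there is nothing to reproduce. The check is of the text first, then an illustration of size.

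**Text check**

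- Section 7.2.6: phone permitted for all five scales; no telephone version, no unscored-item rule, no home or video alternative.
- Section 7.2.1: admission NIHSS by treating physicians, MOCA by certified staff; nothing on phone administration.
- Section 7.3 and Section 9.4: Day 90 scales belong to the follow-up visit; mode is not mentioned.
- Section 8.3: no mode term, no missing-item rule, no sensitivity analysis by mode.
- Section 9.2: NIHSS and MOCA are among the reviewed outcomes; mode is not mentioned.

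No section fills the gap left by Section 7.2.6. The case report form is not among the documents, so whether it has a mode field is unknown; the plan does not require one.

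**How many values could be involved**

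Inputs: 44 analysed patients, 22 per arm (Section 8.2); phone share assumed to be 15-40%, since the documents give none.

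- 0.15 × 44 = 6.6 and 0.40 × 44 = 17.6, so about 7 to 18 values on each scale.
- Section 8.2 expects about 30% stroke mimics. If only true strokes were phoned, the base is 44 × 0.70 = 30.8, giving 0.15 × 30.8 = 4.6 and 0.40 × 30.8 = 12.3, so about 5 to 12.

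**What a mode shift would do to the arm contrast**

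Assumptions: phone scores differ from clinic scores by a constant s (in SD units); f is the share phoned in an arm; 22 per arm; normal approximation on a continuous score; two-sided alpha 0.05. Section 9.1 mentions an alpha but gives no value.

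- Bias = s × (f_control − f_PGZ)
- SE = √(2/22) = 0.302 SD
- Type I error = Φ(−1.96 − bias/SE) + 1 − Φ(1.96 − bias/SE)

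| Phoned, PGZ vs control | s = 0.25 | s = 0.5 | s = 1.0 |
|---|---|---|---|
| 10% vs 10% | bias 0; 0.050 | bias 0; 0.050 | bias 0; 0.050 |
| 10% vs 20% | 0.025; 0.051 | 0.05; 0.053 | 0.10; 0.063 |
| 10% vs 30%, or 20% vs 40% | 0.05; 0.053 | 0.10; 0.063 | 0.20; 0.102 |

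Each cell gives bias in SD, then type I error. Worked example for the last cell: 1.0 × (0.30 − 0.10) = 0.20; 0.20/0.302 = 0.663; Φ(−2.623) + 1 − Φ(1.297) = 0.0044 + 0.0973 ≈ 0.102.

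With equal shares the bias is zero whatever s is. The model covers a constant shift only; it does not describe loss of information if unobserved items are filled with a default value.

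**The case against.** The strongest reply is that Section 7.2.6 is permissive. It says the assessments may be done by phone, does not order anyone to score what cannot be observed, and does not say that phone and clinic scores are to be pooled. The same five scales are listed for discharge in Section 7.2.5, so the phone sentence may simply have been placed ahead of a generic visit list. That is a fair account of how the text may have arisen. It does not remove the problem: NIHSS and MOCA are expressly within the permission, and nothing tells the assessor or the analyst how to treat the result.

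A reader might infer that the sickest patients are the ones phoned. The text refers only to inability to travel, which also covers distance, transport or lack of a companion. Entry needs an NIHSS of only 2 or more (Section 3.1), and expected mimics stay in the study. A link between mode and outcome is plausible, not documented.

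A reader might also infer that phoned patients will look too well, and that the treatment difference will shrink. That needs evidence that unobserved items are scored as normal; the documents offer none, and blank or carried-forward items are equally possible.

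Nor does the type I error of 0.102 describe this trial. It comes from an assumed imbalance in phone shares. If treatment does not affect who can travel, randomisation makes the shares equal in expectation and the expected bias under a constant shift is zero.

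Section 4.1 pairs the NIHSS with an examination ("all stroke patients have a neurological examination and are assessed using the NIHSS and the mRS as part of their routine care"), but this concerns presentation. It supports the general point about the instrument, not how it is scored at Day 90.

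Finally, this is an exploratory pilot of 50, and phone assessment by mRS, BI and GOS is not in question. That limits the seriousness. But no scale is designated as the lead outcome, so NIHSS and MOCA cannot be treated as marginal.

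**Conclusion.** The point holds as a gap in outcome measurement. The plan permits NIHSS and MOCA values that are partly unobserved, does not mark them, and compares them with in-person admission values. This rests on the wording of Section 7.2.6, on the absence of any resolving text elsewhere, and on the nature of the two instruments.

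The size is unknown. The counts above depend on an assumed phone share, and the bias table on assumed shifts and imbalances. The documents do not support a stated direction of bias, a claim that the worst outcomes are the ones affected, or a claim that type I error is inflated. The change should be made because it is cheap and because an unmarked phone score cannot be repaired afterwards; the gap does not invalidate the trial.

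**What to change.** 1. In Section 7.2.6, limit the phone option to scales that can be scored by interview: mRS, BI and GOS. Do not record a full NIHSS or full MOCA by phone; mark each as not done, with the reason the patient did not attend. Alternatively, name a telephone-suitable version in advance and analyse it separately. Split the row in the Schedule of Study Activities to match.
2. Record the mode of assessment for every Day 90 scale and report it by arm.
3. In Section 8.3, add a sensitivity analysis for NIHSS and MOCA that treats the missing values of phone-followed patients as possibly informative. A worst-rank analysis is one example. It is an extreme case, since some of these patients may be absent only for distance or transport, and the recorded reasons help readers judge it.
4. Rely on mRS, BI and GOS for the comparison that includes all followed patients.

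The cost is a few sentences, one mode field, a reason field and one added analysis. The real downside is that some NIHSS and MOCA values become openly missing, possibly informatively. Section 8.3 has no missing-data rule at present, so step 1 without step 3 would exchange one problem for another.

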7.3 Duration of Participation

The total duration of study participation for each subject will be approximately three months, which consists of:

- Screening and enrollment period (within 18 hours of stroke symptom onset)
- Treatment period of 72 hours (3 days)
- A 90 day follow-up visit occurring during the standard of care outpatient visit to the neurology clinic.

7.4 Test Article(s) (Study Drug(s) and/or Study Device(s))

7.4. 1 Description

Pioglitazone hydrochloride 45mg tablets will be overencapsulated to match placebo capsules for this study.

Pioglitazone, a peroxisome proliferator-activated (PPAR γ) receptor agonist, is FDA-approved as an anti-glycemic agent for the treatment of type-2 diabetes that has shown promise for secondary stroke prevention in clinical stroke trials [3-5], but has thus far not been studied as an acute intervention for acute diabetic stroke. PGZ acts primarily by decreasing insulin resistance.

7.4. 2 Treatment Regimen

Following oral administration, PGZ is first measurable in serum within 30 minutes, with peak concentrations observed within 2 hours. It is relatively insoluble but can be crushed and given through a feeding tube. Serum concentrations of total PGZ (PGZ plus active metabolites) remain elevated 24 hours after a once daily dosing.

The treatment group will receive 45 mg of PGZ orally within 18 hours of stroke symptom onset or last known well and subsequently at 24h and 48h after the initial dose. This represents the highest recommend dose in humans and is selected to achieve the highest blood concentration of PGZ as quickly as possible following the stroke event. The control group will receive placebo orally at the same time points. Both groups will be treated identically and receive best standard of care.

Some acute ischemic stroke patients experience trouble swallowing (dysphagia), and all stroke patients are therefore routinely assessed for dysphagia as part of their routine clinical care. If patients are not able swallow, PGZ/placebo will be crushed and administered via a feeding tube.

To avoid unblinding of the study team if the capsules have to be opened/crushed for administration, a warning label will be placed on study drug package telling the bedside nurse not to reveal the contents of the capsule to study team members. Study team members will not administer drug to any patients who are unable to swallow.

There is no provision to provide study treatment after the study.

7.4. 3 Method for Assigning Subject to Treatment Groups

Participants will be randomized to either PGZ or placebo using an equal allocation ratio (1:1). The randomization will be performed using a random number generator via the PLAN procedure within SAS software, version 9.4 (SAS Institute Inc., Cary, NC). Personnel in the Department of Public Health Sciences (PHS) will use the PLAN procedure within SAS software to generate a randomization list using variable-size, random permuted blocks to ensure that the number of participants in each arm is balanced after each set of B randomized participants, where B is the block size. Personnel in PHS will choose the block sizes without revealing it to any of the investigators or study personnel who will be collecting and reviewing outcomes data. The PHS generated randomization list will be provided to Investigational Drug Services (IDS) who will be implementing the randomization for this trial.

7.4. 4 Subject Compliance Monitoring

Nursing staff will chart administration of study drug into the patient's EMR and study personnel will monitor and document the completion of all study procedures.

7.4. 5 Blinding of the Test Article

The investigators, study staff, subjects, and caregivers will be blinded to the subject's treatment assignments for the duration of the trial. Investigational pharmacy will be placed the investigational product into a plain capsule to insure that the investigative team remains blinded (see Section 7.4.6.3). To avoid unblinding of the study team members, if the capsules have to be

opened/crushed for administration by nursing staff, a warning label will be placed on study drug package telling the bedside nurse not to reveal the contents of the capsule to any study team member. Study team members will not administer any study drug.

All blood samples will be coded to maintain masking prior to analysis. The laboratory staff will be unaware of the condition and the treatment of the participants for whom they will conduct the assays as the samples will be identified only with a study number.

The results of the laboratory measurements will not be shared with the treating physicians, and will not impact patient care.

7.4. 6 Receiving, Storage, Dispensing and Return

7.4 .6.1 Receipt of Test Article

The IDS pharmacy will obtain commercially available Pioglitazone 45mg tablets from a pharmacy wholesaler, and pharmaceutical grade empty gelatin capsules and USP grade methylcellulose from an appropriate pharmacy supplier. IDS pharmacy will then compound the active pioglitazone 45mg and matching placebo capsules.

7.4 .6.2 Storage

The study drugs will be stored at controlled room temperature in the pharmacy department with the inpatient IDS study medications.

7.4 .6.3 Preparation and Dispensing

IDS pharmacy will compound the active capsules as follows: the 45mg pioglitazone tablets will be split and placed in an empty gelatin capsule with filler (USP grade methylcellulose). The placebo capsules will be compounded by placing USP grade methylcellulose in an empty gelatin capsule. IDS pharmacy will maintain compounding records for each batch of active and placebo capsules compounded and drug accountability logs for all study medications prepared and dispensed. The compounded capsules will be marked with an appropriate expiration date and expired capsules will be removed from study inventory and destroyed as per the IDS Destruction Policy.

Study treatment capsules (PGZ or placebo) will look identical.

Once a subject has consented and enrolled in the study, confirmation of consent and a study order will be sent to the pharmacy. Pharmacy will then randomize the subject and dispense the 3-day supply of the study medication to the study team for delivery to the subject's nurse. The study medication will be labeled in a blinded manner.

Once the study drug is prepared for the subject, it can only be administered to that subject by the patient's bedside nurse.

7.4 .6.4 Return or Destruction of the Test Article

Once the study drug is prepared for the subject, it can only be administered to that subject. If a subject is withdrawn from the study (See section 3.3), the study drug will be returned to IDS and it will be destroyed according to the IDS drug destruction policy.

7.4 .6.5 Prior and Concomitant Therapy

A concomitant therapy is any medication which is administered between study enrollment and the end of the study drug treatment phase. All concomitant therapies will be monitored daily and recorded by study team members during the duration of the treatment phase with the study drug.

Precautions: PGZ is metabolized in the liver. Therefore, any drug which is a strong CYP2C8 inhibitor or inducer may affect the efficacy of PGZ. Subjects who require these medications during study drug treatment are permitted into the study with additional monitoring/precautions in place:

1. Strong CYP2C8 inhibitors (such as gemfibrozil) increase PGZ concentrations. Therefore, gemfibrozil will be held for the 3 day duration of the study treatment and started after 24 hours of the last dose of study drug.
2. CYP2C8 inducers (e.g., rifampin) may decrease PGZ concentrations. Therefore, these medications will be spaced 4 hours after administration of the study drug.

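### Opened capsules probably show the bedside nurse the arm, and the warning label shields only the study team, so the stated blinding of subjects and caregivers is not secured for tube-fed patients

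*Combined protocol and SAP*

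**What the plan says.** The blinding claim in section 7.4.5 is broad: "The investigators, study staff, subjects, and caregivers will be blinded to the subject's treatment assignments for the duration of the trial".

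Section 7.4.6.3 gives the two recipes. For active drug, "the 45mg pioglitazone tablets will be split and placed in an empty gelatin capsule with filler". For control, "The placebo capsules will be compounded by placing USP grade methylcellulose in an empty gelatin capsule". It then states the matching: "Study treatment capsules (PGZ or placebo) will look identical". It says nothing about how the contents compare once a capsule is opened.

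Section 7.4.2 provides for dysphagia: "If patients are not able swallow, PGZ/placebo will be crushed and administered via a feeding tube". Section 7.4.5 assigns the opening or crushing to nursing staff. Section 7.4.6.3 says of the dispensed drug that "it can only be administered to that subject by the patient's bedside nurse".

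There are two safeguards for opened capsules. The first is a label on the package, described in section 7.4.2 as "telling the bedside nurse not to reveal the contents of the capsule to study team members" and in section 7.4.5 as "telling the bedside nurse not to reveal the contents of the capsule to any study team member". The second is that the study team does not give the drug. The two sections word this second rule differently: 7.4.2 limits it to patients who cannot swallow, and 7.4.5 applies it to all study drug.

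**The concern.** The people stated to be blinded are a wider group than the people the label protects. Where a capsule is opened, the nurse is likely to learn the arm and is told only to keep it from the study team. Nothing tells the nurse to keep it from the patient, the family or the treating physicians.

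Two things are at stake. The first is outcome scoring: improvement at three months is a primary objective (section 1.2), and NIHSS and mRS are among the scales used. If a treating clinician who has learned the arm scores them, the comparison is open to bias. The second is co-treatment. Section 10.0 notes that background insulin or secretagogue doses may need lowering alongside pioglitazone, so a care team that knows the arm has a protocol-stated reason to manage the two groups differently. Glucose, insulin, infection and discharge disposition are all measured or reviewed in this trial (sections 7.1 and 9.2), and section 7.4.2 says that both groups get the same care.

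**Working it through.** The protocol gives no figure to reproduce here. The check sets the provisions side by side, with one calculation for scale.

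**1. Do the opened contents differ?** Active: split tablet plus methylcellulose. Placebo: methylcellulose only. No grinding of the active tablet and no dummy tablet in placebo is described (section 7.4.6.3). That the difference can be seen is an inference from tablet pieces against plain filler. The protocol appears to share it, because a label against revealing the contents is needed only if the contents can give the arm away.

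**2. Who sees them?** The bedside nurse, by sections 7.4.5 and 7.4.6.3.

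**3. Who is protected from hearing about it?**

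| Group | Stated as blinded in 7.4.5 | Covered by the label |
|---|---|---|
| Investigators and study staff | yes | yes |
| Subjects | yes | no |
| Caregivers (term not defined) | yes | no |
| Treating physicians outside the study team | not named | no |

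**4. What does 'caregivers' mean?** If it includes bedside nurses, the stated blinding probably does not hold for any nurse who opens a capsule. If it means family carers, they are unprotected but not necessarily unblinded. Section 7.2.1 lists care givers separately from treating physicians, and section 9.1 mentions a main caregiver alongside the legal representative. Both favour the family reading. On either reading the procedure falls short of the statement.

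**5. Who scores the scales?** Section 7.2.1 gives NIHSS and mRS at presentation to the treating physicians, and BI, GOS and MOCA at baseline to certified study personnel. At discharge and Day 90 (sections 7.2.5 and 7.2.6), BI, GOS and MOCA are marked as research-only, NIHSS and mRS are not, and no scorer is named. Treating clinicians may therefore score the last two.

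**6. Scale.** The tube-fed share is not given; section 7.4.2 says only that some patients have dysphagia. Assume 10% to 50% of the 50 planned patients (section 8.1), with three doses each (section 7.4.2):

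- patients: 0.10 × 50 = 5, to 0.50 × 50 = 25
- capsules opened at the bedside: up to 5 × 3 = 15, to 25 × 3 = 75

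These are illustrations of an assumption, not estimates.

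**The case against.** The strongest reply is that the protocol saw this risk and dealt with it. It labels the package and keeps the study team away from dosing patients who cannot swallow, and the laboratory works on coded samples. That stands: the protected group includes the personnel named for BI, GOS and MOCA, and the gap lies in the label's reach and the capsule recipe.

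A reader might go further and infer that caregiver blinding simply fails, that outcome assessment is unblinded, or that the problem sits in the most severe patients, who dominate the results. The documents do not support those readings.

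- 'Caregivers' is undefined and probably means lay carers, so the accurate statement is that their blinding is not secured.
- Treating physicians are assigned NIHSS and mRS only at presentation, before any dose. Later scorers are unnamed, and some treating physicians may be on the study team and so already covered by the label.
- Day 90 is an outpatient visit about three months after dosing, so bias there would need disclosure that was charted or remembered.
- No link between tube feeding and severity is stated, and no tube-feeding rate is given. Entry requires an NIHSS of only 2 (section 3.1), and about 30% are expected to be stroke mimics (section 8.2), so the upper end of the assumed range may be high.
- Glucose monitoring follows the standard-of-care protocols, and nothing shows that the nurse decides on antibiotics or discharge.

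A sensitivity analysis by route would add little. At an assumed 20% share there would be 0.20 × 50 = 10 tube-fed patients, about 5 per arm. If route tracks severity, unblinding and severity could not be separated.

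These limits bear on the size of the problem. The mismatch between statement and procedure remains.

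**Conclusion.** The point holds in a limited form. On the protocol's own recipe, a nurse who opens a capsule can probably identify the arm. The label stops that knowledge only from reaching the study team, so the blinding claimed for subjects and caregivers lacks a safeguard in tube-fed patients, and treating physicians are outside it too.

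This rests on one inference (split tablet in filler can be told from filler alone, as the label implies) and one open question (who scores NIHSS and mRS after dosing). The number affected cannot be derived from the documents, and no bias in any outcome has been demonstrated. It is worth correcting because the pilot is meant to inform a larger trial (sections 2.3 and 8.2) and the correction is cheap.

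**What to change.** 1. **Sections 7.4.2 and 7.4.5, label.** Bar disclosure of capsule contents to anyone, naming treating physicians, the patient and family as well as the study team. State whether 'caregivers' includes bedside nurses.
2. **Section 7.4.6.3, compounding.** Have the investigational pharmacy grind the active tablet into the same filler, after checking that the opened contents match placebo, or otherwise make them indistinguishable. If that cannot be done, narrow the blinding statement in 7.4.5 to exclude the nurse who opens the capsule.
3. **Sections 7.2.5 and 7.2.6, scorers.** State that NIHSS and mRS at discharge and Day 90 are scored, where feasible, by the blinded certified study personnel used for BI, GOS and MOCA. Confirm that those personnel also cover the later visits, since section 7.2.1 names them only for baseline.
4. **Data collection.** Record which patients had capsules opened, for descriptive reporting only.
5. **Consistency.** Reconcile 7.4.2 and 7.4.5 on whether study team members give no study drug at all or only none to patients who cannot swallow.

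Cost: slightly more compounding work with a one-off matching check, revised label text, one data field, and some scoring time from study staff. Whether ground tablet will match plain filler is not known from the documents, which is why item 2 carries a fallback.
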